1 Using a teachable moment communication process to improve outcomes of quitline referrals  
2  
3 Principal Investigator: [name], PhD,  
4 Department of Family Medicine  
5 Oregon Health & Science University  
6 [name]  
7 [name]  
8 [contact]  
9  
10 Site Principal Investigator: [name], MD, MS, MetroHealth Health System  
11 [name]  
12 [name]  
13  
14 Co-Investigators:  
15 [name], PhD, MetroHealth  
16 [name], MD, MetroHealth  
17 [name], PhD, MPH, Case Western Reserve University  
18 Study Staff:  
19 [name], MS, MBA, MetroHealth  
20 [name], MPA, Case Western Reserve University  
21 [name], MPH, Case Western Reserve University  
22  
23 Institution receiving the PCORI award: Oregon Health & Science University, Portland Oregon, USA  
24  
25 PCORI award number: IHS-1503-29879-IC  
26 ClinicalTrials.gov registration: NCT02764385  
Last updated December 11, 2020  
27

28 **Project summary**

29 **Background:** Guidelines urge primary care practices to provide routine tobacco cessation care.  
30 Implementation of effective and sustainable strategies is lacking, especially for socially and economically  
31 disadvantaged populations. We test a systems-based approach that engages the medical assistant that  
32 assesses the patient's vital signs at the beginning of a routine visit and the added effect of a clinician-  
33 based approach that draws on a relationship-centered communication strategy.

34 **Objectives:** This project aimed to: 1) Improve delivery and documentation of smoking cessation care to  
35 disadvantaged patients using an Ask-Advise-Connect (AAC) systems-based approach, 2) Test the effect  
36 of combining the clinician-based Teachable Moments Communication Process (TMCP) intervention with  
37 AAC on advice to quit, referrals to cessation counseling and provision of tobacco cessation medications  
38 and 3) Examine the narratives of patient subgroups to understand and improve the referral experience.

39 **Methods:** This study engaged a healthcare system and eight primary care clinical sites with two  
40 interventions. The 3-month period before the AAC intervention represented a pre-AAC control period  
41 (baseline). All sites received the AAC strategy throughout the study and its use was evaluated for a  
42 minimum of 6 months (AAC-only). Next, using a group-randomized stepped-wedge design, sites received  
43 the TMCP intervention (AAC+TMCP). The patient population is 40% Medicaid, 23.9% Medicare, 6.1%  
44 uninsured and 30% commercially insured. The AAC strategy involved changes to the electronic health  
45 record (EHR), a new role for medical assistants and a new capacity to send electronic referrals to the  
46 Quitline (QL) to enroll patients in tobacco cessation counseling. Next, in accord with their practice's  
47 place in the stepped wedge design, 44 of the 60 eligible clinicians attended training in the TMCP, an  
48 approach to counseling patients to quit tobacco aligned with patient readiness. Generalized linear  
49 models tested the effect of interventions on immediate outcome measures of process, including  
50 delivery of advice, offer of assistance and referrals accepted, and QL contact and enrollment rates.  
51 Receipt of tobacco cessation medications and quit attempts were also assessed. The primary outcome  
52 was QL contact. In-depth interviews were conducted with 55 patients referred to the QL to explore their  
53 experiences and identify opportunities to improve the referral process.

54

55

56

57

58

59

60  
61  
62  
63  
64  
65  
66  
67  
68  
69  
70  
71  
72  
73  
74  
75  
76  
77  
78  
79  
80  
81  
82  
83  
84  
85  
86

87 **Rationale & background information**

88 Smoking is the leading cause of preventable mortality. Smoking rates in the United States have  
89 declined, but remain particularly high among socially and economically disadvantaged populations, who  
90 are also less likely to use supports for quitting smoking. Therefore, implementing and evaluating  
91 strategies that work for socially and economically disadvantaged populations is a high priority. Among  
92 U.S. smokers, 59% report seeing a primary care clinician at least yearly, making primary care a major  
93 avenue for providing tobacco cessation assistance tailored to each patient's medical history. However,  
94 evidence-based interventions addressing tobacco cessation are generally underused. New healthcare  
95 policy initiatives, requiring assessments of tobacco use and assistance to quit, call for integration of  
96 tobacco cessation interventions into primary care.

97 Referral to quitlines (QLs) that provide evidence-based, effective and cost-efficient assistance with  
98 smoking cessation, is recommended as an effective strategy for tobacco cessation assistance.  
99 However, a clinician's recommendation to call a QL typically results in poor calling rates (range 1.6% -  
100 19%). Yet, success rates increase when QLs proactively call patients after receiving a direct clinician  
101 referral (by fax or electronically). Still, clinicians underutilize direct referrals, potentially due to low  
102 integration of the referral system into the office workflow. Research demonstrates the feasibility of  
103 closed loop electronic referrals using the electronic health record (EHR) for connecting with QLs. The  
104 advantage of eReferral is that patient information is securely transmitted between the referring clinician  
105 and the QL, and QL enrollment and counseling completion records become part of the patient medical  
106 record.

107 Two intervention approaches for providing patients with assistance for smoking cessation have  
108 shown promise in the primary care setting. Ask-Advise-Connect (AAC) is a systems-based approach that  
109 uses the EHR to remind clinicians to ask about tobacco use and give advice to quit, and then  
110 electronically connects interested smokers to tobacco cessation counseling services such as the QL. The  
111 Teachable Moment Communication Process (TMCP) is a relationship and communication-focused  
112 strategy designed to counsel patients about behavior change by responding in a way both appropriate  
113 to and aligned with patient's readiness for a change. These approaches are feasible, complementary  
114 and have the potential to be integrated into a health system to improve sustainability.

[figure not shown]
115 Ask-Advise-Connect (AAC): This proactive, direct messaging EHR-to-QL referral approach has been  
116 shown to increase the number of tobacco users receiving QL treatment by 13- to 30-fold. However, a  
117 major drawback of AAC is a low rate of contacting referred patients. Prior studies found that the QL was  
118 able to contact less than 42% of referred patients. This poor contact rate diminishes the sustainability of  
119 the approach, and is likely due to referring patients inappropriately, ignoring cessation readiness.

120 In this study, we assess the patient's readiness to quit and willingness to be connected to the QL prior to  
121 making an eReferral, thereby assuring appropriate referrals. A drawback of some studies of AAC  
122 implementation strategies is that they rely on study research staff to carry out a key step rather than  
123 a design that is fully integrated and sustainable in a clinical practice. In this study, we train MAs/nurses  
124 to implement the AAC, and modify EHR functionality to facilitate an eReferral, thereby providing a more  
125 sustainable approach.

126 Teachable Moments Communication Process (TMCP): With the TMCP, smoking talk is initiated in an  
127 opportunistic way so that it fits into the flow of addressing problems during a primary care visit. In  
128 providing cessation advice, TMCP calls for clinicians to convey concern, express optimism and  
129 partnership, and recommend quitting tobacco. Finally, central to this approach is eliciting an honest  
130 assessment of the patient's level of cessation readiness and responding in alignment with this readiness.  
131 Research shows that the TMCP approach increases patient motivation to make a quit attempt. Evidence  
132 is accumulating that the TMCP intervention is feasible in primary care and acceptable to patients and  
133 clinicians, leading to significant increases in clinicians' use of recommended counseling behaviors and  
134 activating patients during primary care visits.

135 We propose that the AAC and the TMCP interventions have mutually complementing strengths, and  
136 their combined implementation might synergistically boost positive outcomes. The AAC intervention is  
137 designed to be deployed at every visit so that all patients are assessed for smoking status, advised to  
138 quit, assessed about readiness to quit, and given the opportunity to receive assistance. Since it is a part  
139 of every office visit, the AAC can reach a large percentage of patients. The TM intervention, in contrast,  
140 is situation-specific and driven by identification of and clinician action on a salient concern that arises  
141 during the visit. By leveraging concerns that are salient to the patient, the TMCP can activate patients to  
142 move forward along the readiness to quit continuum. It also reinforces the value of quitting by  
143 incorporating clinician advise to quit, which has been shown to increase quit rates. If implemented  
144 together, these intervention could have a synergistic effect (see Figure 1) whereby the interventions  
145 operate at different levels of influence to mutually reinforce each other. Their combined effect has great  
146 potential to increase the proportion of appropriate referrals (i.e., eligible and ready patients) to the QL,  
147 increase the likelihood of successful patient contact and enrollment, positively affect patients' ratings of  
148 the experience, and support positive movement towards cessation.

Figure 1. AAC and TMCP conceptual model

150

151 **Study goals and objectives**

152 1. Improve delivery and documentation of smoking cessation advice and assistance to socially and  
 153 economically disadvantaged patients using an Ask-Advise-Connect approach integrated into the EHR.  
 154 2. Test the effect of combining the TMCP with AAC on process outcomes, QL referral outcomes and  
 155 smoking outcomes.  
 156 3. Examine the narratives of subgroups of individuals to better understand the referral experience and  
 157 identify ways to improve it.

158

159 **Study Design and Timing.** This study involves two interventions. This report is focused on the TMCP  
 160 intervention and the AAC information is provided for context. The full report will be publically available  
 161 on the PCORI website after the 12-month embargo period passes.

[figure not shown]
162 The AAC was conducted first at the clinic-level and the TMCP was conducted second at the clinician-  
 163 level. It also includes qualitative data collection to complement the quantitative evaluations. Figure 2  
 164 illustrates the three main data collection sources (EHR, patient surveys, and in-depth interviews) and the  
 165 three time periods of data collection (pre-AAC, AAC-only, and AAC+TMCP). The 3-month period before  
 166 the AAC intervention represented a pre-AAC control period (baseline). Both interventions were  
 167 implemented using a stepped wedge design, as indicated in Figure 2. The start date represents the date

168 of the first clinic's exposure to the interventions. The step graphic between each condition represents  
169 the starting points for each of the clinics' exposure to the interventions. This design allowed us to test  
170 the additional impact of TMCP beyond the gains realized via AAC across all of the clinics by the end of  
171 the step-wedge implementation. On a rolling basis, data collection indicated the intervention exposure  
172 statuses for each clinic and assessed visit level process outcomes.

[figure not shown]
173 Figure 3 provides more detail about the timing of the AAC and the TMCP intervention  
174 implementation at each of the 8 sites. AAC was the first intervention implemented, and the AAC training  
175 at the first clinic was conducted on February 15, 2017. This training was then conducted at the other  
176 seven clinics at approximately 2-week intervals, but the timing of the training was not randomized.  
177 Trainings were scheduled during regularly scheduled monthly staff meetings for each clinic. The training  
178 date was noted such that a period of pre- and a period of post-training could be defined for each clinic.  
179 Approximately 6 months after the implementation of the AAC in the last site, the TMCP intervention was  
180 implemented, again in a stepped pattern.

181 For the TMCP, the eight clinics were randomized to an implementation time point using the  
182 following approach. A single digit number was assigned to each site. A list of 100 random single digit  
183 numbers was generated and using this list, as a site number came up in the random list it was assigned  
184 the next sequential time point. We encountered two anomalies with randomization of the sites. First,  
185 after implementing the AAC intervention, the site that was randomized to receive the TMCP training  
186 first lost their practice manager. MetroHealth requested that we delay the implementation of the TMCP  
187 in that site due to challenges with daily operations until a new practice manager was effectively in place.  
188 This site was moved to be last. Second, also after the implementation of the AAC intervention, one of  
189 the sites closed. A replacement site was identified to receive the AAC intervention and was included as  
190 the last site for training for the TMCP. The TMCP implementation time points were scheduled as close to  
191 1-month intervals as possible. The first clinic received the TMCP training on October 25, 2017. The  
192 amount of time a clinic was in any one of the three defined study conditions varied but is accounted for  
193 in the analyses.

194 Figure 2. Schema of data collection time points (for EHR, surveys, and in-depth interviews) across all  
195 sites.

198 Figure 3. AAC and TMCP intervention implementation dates and periods of time before, between and after interventions for each site.

\* Due to technical problems for some clinicians, a second TMCP implementation date was conducted on 11/2

199 \*\* This site was added to replace a site that had been randomized and received the AAC training, but closed shortly after AAC training.

## Research methods

### Participating sites and randomization

Eight community-based primary care practices in a large safety-net healthcare system in Cleveland Ohio participated in this stepped wedge comparative effectiveness study. Using a random number list generated by the study analyst, the sites were randomized to separate intervention time points (1-month intervals) in which all clinicians (MD, DO, NPs) who spend 40% or more of the work week providing patient care were scheduled to attend the TMCP training. The health system requested that the intervention be implemented first in one site. The remaining 7 sites followed the randomization procedure. The principal investigator informed each clinical director of the site's assigned time point and scheduled a training date.

Prior to the baseline period for this study, all eight clinics engaged in an AAC system change initiative to improve the provision of tobacco cessation support. The systems change engaged MAs/RNs to use an EHR supported AAC strategy. The MA/RN role, which normally included Asking about tobacco status, expanded to: 1) Using a brief scripted phrase, to Advise those who use tobacco to quit; 2) Assessing interest in quitting tobacco in the next 30 days; 3) for patients interested in quitting now, asking if they would like assistance to quit from a coach or counselor; and 4) for those choosing assistance, Connecting the patient by an electronic referral (e-referral) sent to either the Ohio Quitline (QL) or to the in-house Freedom from Smoking (FFS) program. Eligibility for free QL services included being aged 18 or older with Medicaid or no insurance, or being pregnant. The QL included up to 5 telephonic counseling sessions and access to web and online chat support. The QL offers nicotine replacement therapy (NRT), if indicated, and with approval from the referring clinician, the NRT is mailed to the patient. Individuals not eligible for the QL were referred to the in-system FFS program – an in-person 8-session group tobacco cessation class offered by the healthcare system. The EHR automatically assessed patient eligibility with payer data and generated the correct referral order in a

process that was seamless for both the MA/RN and the patient. The AAC serves as the comparator for the TMCP.

#### TMCP Training Implementation

The TMCP intervention included a 50-minute web-based module that clinicians completed on office computers, followed by 90 minutes of skills practices with Standardized Patients (SPs) in the practices' exam rooms. Trainings were conducted at the practice sites during a clinical work day with cancellation of 2.5 hours of clinical activity to accommodate the training.

#### Web Module

The web module, based on our previous work, consists of: 1) didactic content describing the TMCP rationale and process; 2) actor-portrayed examples of provider-patient interactions in each step of the TMCP; and 3) learning self-assessments. During the web module, clinicians were asked to interact with the content by repeating certain phrases aloud and thinking about and then saying aloud how they might respond to a patient with a specific level of readiness. Self-assessments (i.e. quizzes) were integrated after each major learning topic. After each question was answered, the clinician was provided with the reason why the response was either correct or incorrect.

The training included skills practices for clinicians to learn each TMCP skill through enactment. Skills practices took place in the clinic exam rooms, providing a realistic setting. The clinician participants rotated through 6-8 different scenarios played by SPs. The SPs were actors with prior SP experience and received five hours of training specific to this study. Each SP was trained to act out two unique 'case scenarios' that they would routinely play in the skills practices. For each skills practice, the clinician was provided basic SP information, such as age, sex, and smoking history. Skills practices were observed by study team members that served as coaches to provide feedback and additional training in technique. Coaches used a checklist of TMCP skills to insure complete assessment and to guide

feedback. Each SP case was also created as a test patient in the EHR so that clinicians could practice using the TMCP document flowsheet with each SP, as described below.

#### Development of document flowsheet

Document flowsheets are EHR tools used to document information in a structured manner. The TMCP flowsheet outlines the steps and phrases for the TMCP for clinicians to use as a guide with patients, eliminating the need to memorize each sequential TMCP step. The flowsheet is also a simple standardized tool to record patient responses with minimal clinician effort. With this tool, both the delivery of TMCP and the recording of patient information are done simply and result in retrievable records for future care.

During the skills training each clinician was shown how to use the TMCP flowsheet and had it added to his/her EHR tool shortcuts. Clinicians were asked to use the flowsheet during the skills practice scenarios to gain experience and comfort with its features. As needed, coaches could address any difficulty clinicians had using the flowsheet during the feedback period after a skills practice. An EHR tobacco cessation order set could be used by providers to order tobacco cessation medication and to order QL or FFS classes and was also reviewed during skills practice.

#### Debriefing about the training and follow-up

Following the completion of the web-module and the skills practices, the providers re-grouped with the research team to debrief about their experiences. Feedback on format, length of training, processes, content etc. were discussed as well as the perceived value overall. Approximately one month after the TMCP training participating clinicians were sent follow-up messages through the EHR that 1) offered reminders about the TMCP, 2) encouraged clinicians to use the TMCP, and 3) provided instruction for using the tobacco cessation flowsheet. Clinicians were invited to respond to messages with questions and or feedback.

#### Study sample

The study sample consists of eight sites, 60 clinicians from those sites and all adult patient visits during the study period. Figure 3 shows the timing of the training and implementation of the TMCP interventions at each of the eight study sites. Study data collection began August 2016 and concluded April 2019. One of the original eight clinics that received the AAC training closed shortly afterwards. A replacement site (#8) was identified from a similar neighborhood, and the original clinic was excluded from all analyses. The replacement site received the AAC training and was assigned to receive the TMCP intervention training 1 month after the TMCP training implementation was conducted at the last clinic that had been randomized. This approach allowed sufficient time for data collection and assessment between the implementation of the AAC and the implementation of the TMCP intervention.

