### Measures

Clinician characteristics gathered from the health system included: sex, degree (MD, DO, NP), specialty and years since last clinical training. Patient characteristics including sex, race, ethnicity, insurance type and smoking status, were drawn from the EHR.

TMCP-specific variables include training participation, online learning module completion and quiz score. Use of the TMCP flowsheet by clinicians during visits was measured for 6-months after training to indicate use of the TMCP. Clinician's documentation of any portion of the TMCP flowsheet was counted as 'use'.

Outcome measures include contact by the QL or FFS among those patients that accepted a referral and provision of brief advice. Secondary outcomes include medication orders (i.e. varenicline, bupropion or nicotine replacement therapy) enrollment among those referred to cessation support (QL or FFS), and quit attempts. For this study, a quit attempt is defined as a change in smoking status from current smoker to former smoker and documentation of a quit date in the EHR. Quit attempts are evaluated for all smokers.

We report the rates of Ask, Advise, Assessment of readiness to quit and acceptance of a referral (Connect) to tobacco cessation assistance for the AAC intervention (AAC only) period and the time period after the TMCP intervention (AAC+TMCP). Each of these indicators is measured from discrete fields in the EHR. As shown in Figure 1, the timing of the AAC and the TMCP intervention implementation and the time periods between the two interventions varied.

We assessed patients' experiences with the clinic's processes. The survey samples included at least 17 smokers from each of the eight sites for the AAC only and the AAC+TMCP study periods. Patients who attended a primary care visit during a specified period were invited to complete the survey by web or phone, depending on the participant's preferred contact method. The survey included 11 items about being treated with respect, feeling listened to, and whether the advice was helpful. Responses were measured using a 5- point Likert scale rating from excellent to poor.

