#### Statistical analyses

We describe clinician characteristics and patient visits during the study period, and participation in the training and uptake of the TMCP as documented by flowsheet usage. Analyses compared adjusted rates for the AAC+TMCP intervention to AAC only period using a generalized estimating equation (GEE) approach, with robust estimation of variances. Specifically, we modeled the log odds of a particular outcome of interest for a particular patient as a function of intervention status (AAC only vs. TMCP + AAC) at each time point, incorporating random practice site and clinician effects. Three analyses were conducted: 1) intent to treat, 2) per protocol (i.e. clinicians that participated in the TM training), and 3) per documented use of the TMCP approach in a visit. We report rates of performance, odds ratios (OR) and 95% confidence intervals (95% CI). We used 10% as a minimally important difference. Data analyses were performed April 2019 - August 2020. Because this was an educational intervention for clinicians, all of whom ultimately received the training, neither the clinicians nor the study team could be blinded to the group assignment; this design also made it impossible to blind the analyst to group assignment.

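### Contact and enrolment have no ascertainment window; if visits ran up to the April 2019 close, every under-followed referral falls in AAC+TMCP

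*Combined protocol and SAP*

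**What the plan says.** - **Sample and dates (Study sample).** The sample includes "all adult patient visits during the study period". The only closing date is in "Study data collection began August 2016 and concluded April 2019". The study period itself is given no end date.
- **Outcomes (Measures).** "Outcome measures include contact by the QL or FFS among those patients that accepted a referral"; the secondary outcomes include "enrollment among those referred to cessation support (QL or FFS), and quit attempts". Neither contact nor enrolment has a time limit. The Project summary names quitline contact as the primary outcome. Flowsheet use, by contrast, is limited to six months after training.
- **Roll-out (Study Design and Timing).** "The first clinic received the TMCP training on October 25, 2017", and the other sites followed at roughly monthly steps.
- **Analysis (Statistical analyses).** AAC+TMCP is compared with AAC only, modelling the log odds on intervention status with site and clinician effects. No calendar-time term is listed. "Data analyses were performed April 2019 - August 2020", so analysis began in the month that collection ended.

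**The concern.** Contact and enrolment happen after the visit. The quitline has to reach the patient once the e-referral arrives, and Freedom from Smoking is an in-person class series. A referral made shortly before outcome data close may be counted as not contacted or not enrolled only because observation stopped.

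In a stepped roll-out this loss is not shared between conditions. Every site had been in AAC+TMCP for about 11 months by the close, so any truncated referral is an AAC+TMCP referral. Even the latest AAC-only referral had about 11 months to mature. An open-ended definition therefore gives the two conditions unequal time to show the event, on the outcome named as primary. At stake is an understated TMCP effect on contact, and more so on any slower outcome.

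**Working it through.** The plan states no sample size, event count or lag, so there is no figure of its own to reproduce.

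**Step 1: dates.** Eight starts from 25 October 2017 in one-month steps put the last at about 26 May 2018. These dates are derived, because Figure 3 is not shown. To 30 April 2019, AAC+TMCP lasts 18.1 months at the first site and 11.1 at the last (mean 14.6; total 117.1 site-months).

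**Step 2: loss if visits and outcomes close together.** Assumptions: even referral accrual, exponential time to contact with mean m, the same true contact rate p in both conditions, and a common close on 30 April 2019. With site exposures Lᵢ:

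share of contacts lost = Σ m(1 − exp(−Lᵢ/m)) / Σ Lᵢ, which is close to m divided by the mean exposure.

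Observed rate = p × (1 − share lost). Spurious OR = odds(observed) / odds(p). AAC-only loses practically nothing. The upper rate, p = 0.42, comes from the Rationale, which reports contact below 42% in prior studies. The lower rate, 0.20, and all lags are assumptions.

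| Mean lag | Share lost | p = 0.42: change, OR | p = 0.20: change, OR |
|---|---|---|---|
| 7 days | 1.6% | −0.7 points, 0.97 | −0.3 points, 0.98 |
| 14 days | 3.1% | −1.3 points, 0.95 | −0.6 points, 0.96 |
| 30 days | 6.7% | −2.8 points, 0.89 | −1.3 points, 0.92 |
| 60 days | 13.5% | −5.7 points, 0.79 | −2.7 points, 0.84 |
| 90 days | 20.0% | −8.4 points, 0.70 | −4.0 points, 0.76 |

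Example at 30 days: 0.42 × (1 − 0.0673) = 0.3917, and (0.3917/0.6083) / (0.42/0.58) = 0.89. At p = 0.40, half-month and one-month lags give 38.6% and 37.3% (OR 0.94 and 0.89).

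**Step 3: effect of time terms.** The same scenario was fitted by logistic regression on expected rates, with p = 0.40, no true effect, and AAC starts at two-week steps from 15 February 2017. Fixed site effects stood in for the plan's site and clinician effects.

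| Model | OR, half-month lag | OR, one-month lag |
|---|---|---|
| Site effects only | 0.94 | 0.89 |
| Plus calendar-month indicators | 1.00 | 1.00 |
| Plus a linear time trend | 1.14 | 1.26 |

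Truncation depends on calendar date alone and is concentrated in months when all sites are in AAC+TMCP, so month indicators absorb it. A straight line cannot follow the late drop. The slope is pulled down and the intervention term moves up to compensate.

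**Step 4: if a run-out existed.** Suppose AAC+TMCP visits stopped six months after each site's training while outcomes ran to 30 April 2019. The last site would then have about 5 months of run-out. At p = 0.42 the bias is about 0.0 points for 14- or 30-day lags, 0.3 for 60 days and 1.3 for 90 days.

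**The case against.** The strongest reply is that the shared close is inferred. Study sample dates data collection, which covers EHR data, surveys and interviews, and does not date the last included visit. The two windows already differ at the start. Collection began in August 2016, but a three-month baseline before the first AAC training on 15 February 2017 starts in mid-November 2016. Figure 3 is captioned as showing the periods before, between and after the interventions at each site, and may give the missing end dates; neither it nor Figure 2 is available here. All of this stands, so the point has to be conditional.

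A reader might also infer that no covariate adjustment could help. That is wrong: Step 3 shows that month indicators remove the bias and a linear trend reverses it. The direction against TMCP holds for the model as written. The text says that varying time in condition is accounted for, but names no method.

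A third stronger reading is that truncation could hide or reverse any real TMCP gain. The documents do not support that. They describe quitlines calling patients proactively after a direct referral, which gives no reason to expect long contact lags. A loss of 10 points would need a mean lag of about 108 days at p = 0.42, or 283 days at p = 0.20. The plan's 10% minimally important difference is not said to be absolute or relative. Read as points, no lag in the table reaches it. Read as relative, a 60-day lag does (13.5%).

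None of this supplies the missing window.

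**Conclusion.** The point holds in conditional form. Contact and enrolment have no ascertainment window, and the available text gives neither a last-visit date nor a run-out. If visits were included up to or near April 2019, all under-ascertained referrals lie in AAC+TMCP, and the described model is biased against TMCP.

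For contact at 40-42%, the size is about 1 point for a two-week mean lag and about 3 points for one month (OR about 0.94-0.95 and 0.89). It is under 1 point at one week, and larger for slower outcomes, which may include enrolment. This rests on assumed lags, even accrual, derived step dates and a common close. It identifies a gap in the outcome definition, not a demonstrated bias in the result, and is worth fixing because the remedy is simple and does not depend on how calendar time is modelled.

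**What to change.** In Measures, score contact and enrolment within one fixed window after each accepted referral, the same in both conditions: for example 90 days, or a shorter window set from AAC-only referral-to-contact times. Include only referrals accepted at least that long before the outcome data cut. State the last-visit date and the outcome cut-off date. If a sufficient run-out already existed, stating those dates settles the truncation question.

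**Cost.** If visits ran to April 2019, a 90-day window drops 8 × 3 / 117.1, or about 20%, of AAC+TMCP referrals. Taking precision as proportional to site-months, with a mean of 10.2 months in AAC-only (derived from the AAC and TMCP starts above) and AAC+TMCP falling from 14.6 to 11.6, the interval widens by √[(1/10.2 + 1/11.6) / (1/10.2 + 1/14.6)] = 1.05, or about 5%. A shorter window costs less.

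The rule also needs dated contact and enrolment records, which the documents do not confirm. Because analyses ended in August 2020, it means re-running these two outcomes as well as editing the text.
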